The usual first treatment for NMIBC (Ta, T1, and CIS) is transurethral resection of the bladder tumors (TURBT), followed by intravesical immunotherapy, most commonly with bacillus Calmette-Guérin (BCG). ([Babjuk 2013, American Urological Association 2014](#)) In patients with T1 tumors, a second TURBT is recommended. ([Babjuk 2013, American Urological Association 2014](#)) Induction therapy with BCG is usually dosed as 6 once-weekly instillations. ([Babjuk 2013, American Urological Association 2014](#)) In patients with high-grade Ta, T1, and CIS, maintenance therapy with BCG of at least 1 year is recommended, ([Babjuk 2013, Anastasiadis 2012](#)) although the optimal dose, dosing schedule, and duration of treatment are unknown. ([American Urological Association 2014](#)). Local and systemic side effects are common with intravesical BCG therapy, causing discontinuation of treatment in approximately 20% of patients. ([Sylvester 2011](#)) Approximately 75% of patients experience local side effects (including cystitis, irritative voiding symptoms, and hematuria), while 40% report systemic side effects, including general malaise and fever. ([Sylvester 2011](#)) Intravesical BCG failure occurs in up to 40% of patients. ([Sylvester 2011](#)) Because of the high risk for development of muscle invasive disease, cystectomy is recommended for CIS and high-grade Ta and T1 patients who experience disease recurrence following intravesical therapy. ([Babjuk, 2013, American Urological Association 2014](#)) For patients unable or unwilling to undergo cystectomy, treatment options are limited.

Vicinium™ (Vicinium) contains the active pharmaceutical ingredient VB4-845, which is a recombinant fusion protein produced in *Escherichia coli* (*E. coli*) that expresses a humanized single-chain antibody fragment (scFv) specific for the epithelial cell adhesion molecule (EpCAM) antigen linked to ETA(252-608). ETA(252-608), which is a truncated form of *Pseudomonas* exotoxin A (ETA) that lacks the cell binding domain, is a single polypeptide fusion protein produced by continuous translation of a single construct.

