Of the 134 subjects,  $\geq 77$  will accrue to Cohort 1. Up to 57 additional subjects in total may accrue to Cohorts 2 and 3. This is an outpatient study. All treatments may be administered in the study clinic.

All diagnostic pathology (bladder tissue and urine cytologies and if performed, tissue from prostatic urethral biopsies) will be reviewed and graded by an independent pathologist and cytopathologist with experience in NMIBC diagnoses. The details of sample handling and logistics will be provided in a separate laboratory manual.

The sample used for determining subject eligibility for inclusion into the trial (post-BCG biopsy) must be reviewed and signed off by the pathologist prior to study enrollment and start of study treatment. All other samples will be read in a timely fashion and the results will be available to study investigators via the electronic CRF.

[figure not shown]
Time points for this study will use a week–day convention. For each subject, Day 1 is defined as the date that the subject first receives study drug and will be designated as Week 1 Day 1 (W1D1). The day before this date is Day  $-1$  (W $-1$ D $-1$ ; there is no Day 0).

Each subject's study course consists of a Screening Period, a 12-week Induction Phase, a Maintenance Phase and a Post-Treatment Evaluation. Subjects will receive intravesical Vicinium instillations twice weekly (BIW) for 6 weeks followed by once weekly for 6 weeks for a total of 18 doses in the Induction Phase. The twice-weekly doses are to be administered at least 48 hours apart (and no more than 2 doses may be administered within a calendar week, i.e., within a Sunday through Saturday). During the Maintenance Phase, Vicinium is administered once every other week. Total duration of treatment (combined Induction and Maintenance Phases) is up to 2 years (104 weeks). Subjects with a protocol-defined treatment failure (see [Section 14.2](#)) or other criteria for study drug discontinuation (see [Section 11.3](#)) will be withdrawn from the study.

[figure not shown]
Subjects will be evaluated for disease every 13 weeks ([Figure 1](#), [Section 10.4](#), [Section 10.5](#)). The first on-study evaluation will occur after the Induction Phase. At Week 12, a urine sample for cytology will be collected. In Week 13, subjects will undergo cystoscopy. Subjects without

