EFS is defined as the interval from the date of first dose of study treatment to an event. Subjects who have a treatment failure or die following the post induction visit will be treated as having an event on the date of treatment failure or death. Subjects without evidence of a treatment failure who are diagnosed with upper or lower urinary tract urothelial carcinoma by histology, cytology or radiographic evidence will be censored at the date of diagnosis. Subjects without evidence of a treatment failure who undergo cystectomy will be censored at the date of cystectomy. All other subjects will be censored at the time of last assessment including long-term follow up.

Censoring rules for the analysis of EFS are presented in the table below.

Table: Censoring scheme for EFS

Situation	Date of Event or Censoring	Outcome
Treatment failure	Date of treatment failure	Event
Death without treatment failure and occurring prior to treatment discontinuation	Date of death	Event
Death without treatment failure and occurring after treatment discontinuation	Date of last evaluable disease assessment on or prior to treatment discontinuation ^a	Censored ^a
No baseline disease assessment	Date of first dose	Censored
No on-study disease assessments and no death	Date of first dose	Censored
No treatment failure and no death	Date of last evaluable disease assessment	Censored
New anti-cancer therapy received without treatment failure and reported prior to or on the same day as disease assessment	Date of last evaluable disease assessment on or prior to the date of initiation of subsequent therapy	Censored
Second non-NMIBC cancer reported prior to or on the same day as disease assessment	Date of last evaluable disease assessment on or prior to the date of diagnosis of non-NMIBC cancer	Censored
a This censoring rule acknowledges that disease assessments were not recorded after treatment discontinuation due to an AE.		

Cystectomy-Free Days

Cystectomy-free days is defined as the time from the date of first dose of study treatment to physical removal of the bladder. Subjects who are alive and do not have their bladder removed will be censored at the time of last contact.

Censoring rules for the analysis of cystectomy-free days are presented in the table below.

Table: Censoring scheme for Cystectomy

Situation	Date of Event or Censoring	Outcome
Cystectomy	Date of cystectomy	Event
Death without cystectomy	Date of death	Censored
No cystectomy	Date of last contact	Censored

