3.3.9. Combining Data Across Panels

When data are combined across panels to create composite endpoints, like complete response, information will be combined in the following manner:

1. Data will be merged by visit for each subject.
2. Unscheduled and early termination data will be windowed according to the visit windows below. Additionally, data from visits where pathology, cytology, and cystoscopy are unexpected (i.e., Maintenance Month 4) will be windowed using the table below.
3. Data within a given visit window will be collapsed to the worst-case result. For example, if a subject has two central pathology assessments for a given visit one with 'CIS' and the other with 'No Tumor', the analysis result for the collapsed visit will be considered as 'CIS'.
4. The date corresponding to the collapsed visit will be the earliest observed date for the visit.

Analysis Visit	Study Days
Screening	-8 < Study Day < 1
Week 1	1 <= Study Day <= 49
Post Induction Phase	49 < Study Day <= 137
Maintenance Month 3	137 < Study Day <= 227
Maintenance Month 6	227 < Study Day <= 318
Maintenance Month 9	318 < Study Day <= 409
Maintenance Month 12	409 < Study Day <= 500
Maintenance Month 15	500 < Study Day <= 591
Maintenance Month 18	591 < Study Day <= 682

Maintenance Month 21	682 < Study Day <= 773
Long-term Follow up Month 3	773 < Study Day <= 864
Long-term Follow up Month 6	864 < Study Day <= 955
Long-term Follow up Month 9	955 < Study Day <= 1046
Long-term Follow up Month 12	1046 < Study Day <= 1137
Long-term Follow up Month 15	1137 < Study Day <= 1228
Long-term Follow up Month 18	1228 < Study Day <= 1319
Long-term Follow up Month 21	1319 < Study Day <= 1410
Long-term Follow up Month 24	1410 < Study Day <= 1501

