- 14.2.4.1.5 Cystectomy-Free Days by Race Subgroup – mITT Population
- 14.2.4.1.6 Cystectomy-Free Days by Prior BCG Therapies Subgroup – mITT Population
- 14.2.4.1.7 Cystectomy-Free Days by Instillation Subgroup – mITT Population
- 14.2.4.3 Cystectomy-Free Days – Evaluable Population
- 14.2.4.4 Cystectomy-Free Days – Induction Phase Dosing Compliant Population
- 14.2.4.5 Cystectomy-Free Days – Study Dosing Compliant Population
- 14.2.4.6 Cystectomy-Free Days, Responders vs Non-responders – Primary Efficacy Population
- 14.2.5.1.1 Time to Disease Recurrence – mITT Population – Cohort 3
- 14.2.5.1.2 Time to Disease Recurrence by Age Subgroup – mITT Population – Cohort 3
- 14.2.5.1.3 Time to Disease Recurrence by Gender Subgroup – mITT Population – Cohort 3
- 14.2.5.1.4 Time to Disease Recurrence by Region Subgroup – mITT Population – Cohort 3
- 14.2.5.1.5 Time to Disease Recurrence by Race Subgroup – mITT Population – Cohort 3
- 14.2.5.1.6 Time to Disease Recurrence by Prior BCG Therapies Subgroup – mITT Population – Cohort 3
- 14.2.5.1.7 Time to Disease Recurrence by Instillation Subgroup – mITT Population – Cohort 3
- 14.2.5.3 Time to Disease Recurrence – Evaluable Population – Cohort 3
- 14.2.5.4 Time to Disease Recurrence – Induction Phase Dosing Compliant Population – Cohort 3
- 14.2.5.5 Time to Disease Recurrence – Study Dosing Compliant Population – Cohort 3
- 14.2.6.1.1 Progression-free Survival – mITT Population
- 14.2.6.1.2 Progression-free Survival by Age Subgroup – mITT Population
- 14.2.6.1.3 Progression-free Survival by Gender Subgroup – mITT Population
- 14.2.6.1.4 Progression-free Survival by Region Subgroup – mITT Population
- 14.2.6.1.5 Progression-free Survival by Race Subgroup – mITT Population
- 14.2.6.1.6 Progression-free Survival by Prior BCG Therapies Subgroup – mITT Population
- 14.2.6.1.7 Progression-free Survival by Instillation Subgroup – mITT Population
- 14.2.6.3 Progression-free Survival – Evaluable Population
- 14.2.6.4 Progression-free Survival – Induction Phase Dosing Compliant Population
- 14.2.6.5 Progression-free Survival – Study Dosing Compliant Population
- 14.2.7.1.1 Overall Survival – mITT Population
- 14.2.7.1.2 Overall Survival by Age Subgroup – mITT Population
- 14.2.7.1.3 Overall Survival by Gender Subgroup – mITT Population
- 14.2.7.1.4 Overall Survival by Region Subgroup – mITT Population
- 14.2.7.1.5 Overall Survival by Race Subgroup – mITT Population

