- 14.2.2.4.1 Histogram of Maintaining CR for at Least 1 Year Post-Induction Phase for Subjects with CR at Months 3, 6, 9, and 12
- 14.2.2.4.2 Histogram of Maintaining CR for a Duration of at Least 1 Year for Subjects with CR at Months 3, 6, 9 and 12
- 14.2.2.5 Swim-Lane Plot: Duration of Response
- 14.2.3.2 Kaplan-Meier Plot: Event-free Survival
- 14.2.4.2.1 Kaplan-Meier Plot: Cystectomy-Free Days by Cohort
- 14.2.4.2.2 Kaplan-Meier Plot: Cystectomy-Free Days for Responders vs Non-Responders
- 14.2.5.2.1 Kaplan-Meier Plot: Time to Disease Recurrence – Cohort 3
- 14.2.5.2.2 Swim Lane Plot: Time to Disease Recurrence – Cohort 3
- 14.2.6.2 Kaplan-Meier Plot: Progression-free Survival
- 14.2.7.2 Kaplan-Meier Plot: Overall Survival
- 14.3.4.1.2 Spaghetti Plot: Clinical Laboratory Assessments by Visit – Subjects with a Treatment Emergent Grade 3 or Higher Event
- 14.3.4.1.3 Scatter Plot: Alanine Aminotransferase by Visit vs. Baseline
- 14.3.4.1.4 Scatter Plot: Alkaline Phosphatase by Visit vs. Baseline
- 14.3.4.1.5 Scatter Plot: Aspartate Aminotransferase by Visit vs. Baseline
- 14.3.4.1.6 Scatter Plot: Bilirubin by Visit vs. Baseline
- 14.3.4.1.7 Scatter Plot: Creatinine by Visit vs. Baseline
- 14.3.4.1.8 Scatter Plot: Hemoglobin by Visit vs. Baseline
- 14.3.4.1.9 Scatter Plot: Leukocytes by Visit vs. Baseline
- 14.3.4.1.10 Scatter Plot: Lymphocytes by Visit vs. Baseline
- 14.3.4.1.11 Scatter Plot: Neutrophils by Visit vs. Baseline
- 14.3.4.1.12 Scatter Plot: Platelets by Visit vs. Baseline

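### Cystectomy-free days are compared by response from first dose, although response is first assessed at about Week 13; cystectomies before that visit bias the comparison towards responders

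*SAP*

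**What the plan says.** The SAP's list of final outputs (Section 12) includes Table 14.2.4.6, "Cystectomy-Free Days, Responders vs Non-responders", in the Primary Efficacy Population, and Figure 14.2.4.2.2, "Kaplan-Meier Plot: Cystectomy-Free Days for Responders vs Non-Responders". Section 4.3 makes that population every treated subject with CIS; it is not limited to those whose bladder is intact at the first evaluation.

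The time origin is in SAP Section 3.3.7: "Cystectomy-free days is defined as the time from the date of first dose of study treatment to physical removal of the bladder". On censoring, the same section says: "Subjects who are alive and do not have their bladder removed will be censored at the time of last contact". Its censoring table also censors death without cystectomy at the date of death.

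Response comes later. Protocol Section 10 says "The first on-study evaluation will occur after the Induction Phase" and "In Week 13, subjects will undergo cystoscopy". SAP Section 3.3.9 gives the post-induction visit the analysis window "49 < Study Day <= 137".

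SAP Section 5.2.1 classifies response in four steps. Failing central pathology or cytology is a failure. A failure stays a failure. A subject who has discontinued the study and lacks the data needed for response is not a complete responder. Anyone left is a complete responder. Section 5.2.5 names only Kaplan-Meier for cystectomy-free days. No landmark, time-dependent covariate or caution is attached to the comparison, and the SAP does not say whether responder means response at Month 3 or at any visit.

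**The concern.** The groups are formed by a result that does not exist until about Week 13, while the clock starts on Day 1. To be assessed as a responder, a subject normally has to reach the evaluation with the bladder in place. A subject whose bladder is removed earlier normally cannot be a responder, and the event lands in the non-responder curve. This is guaranteed-time (immortal-time) bias: it can separate the curves even if response has no bearing on later cystectomy.

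The plan does not assume that surgery only follows an assessed failure. The EFS rules in both documents provide for cystectomy without treatment failure.

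These are the only listed outputs that relate response to bladder removal, so a visible gap is likely to be read as response sparing bladders. Part of that gap could be an artefact of the time origin.

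**Working it through.** **No plan figure to reproduce.** The documents give no event count, cystectomy rate or effect size for this comparison. The check asks what gap would appear if response and cystectomy were unrelated.

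**Inputs**
- From the documents: origin at first dose; first evaluation in Week 13, taken as Day 91, so t = 91/365.25 = 0.249 years.
- Assumed: annual cystectomy rate r after the evaluation, 5-30%; f, the ratio of the hazard before Day 91 to the later hazard; p = 40% responders among those with the bladder intact at Day 91. For comparison, Protocol Section 7 reports 44% complete response (20/45) in Phase 2.
- All cystectomies before Day 91 are assigned to non-responders.

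**Formulas**, with λ = −ln(1 − r) per year:
- Bladder intact at Day 91: S = exp(−f·λ·t)
- Responders, cystectomy-free at 12 months: R = exp(−λ·(1 − t))
- Non-responders: N = (1 − p)·S·R / (1 − p·S)
- Gap = R − N = R·(1 − S) / (1 − p·S)

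The gap carries the factor 1 − S, the share with a cystectomy before the evaluation. If that share is zero, the gap is zero.

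**Worked case, r = 15%** (λ = 0.1625, R = 0.8851)
- f = 1: S = 0.9603; gap = 0.8851 × 0.0397 / (1 − 0.4 × 0.9603) = 0.0351 / 0.6159 = 5.7 points.
- f = 0.5: S = 0.9800; gap = 0.8851 × 0.0200 / (1 − 0.4 × 0.9800) = 0.0177 / 0.6080 = 2.9 points.
- f = 0: S = 1; gap = 0.

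**Spurious 12-month gap (percentage points), p = 40%**

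| Early hazard relative to later (f) | r = 5% | 10% | 15% | 20% | 30% |
|---|---|---|---|---|---|
| 1 | 2.0 | 3.9 | 5.7 | 7.4 | 10.3 |
| 0.5 | 1.0 | 2.0 | 2.9 | 3.8 | 5.4 |
| 0.25 | 0.5 | 1.0 | 1.5 | 1.9 | 2.8 |
| 0 | 0 | 0 | 0 | 0 | 0 |

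At f = 1 the share with a cystectomy before Day 91 is 1.3, 2.6, 4.0, 5.4 and 8.5%, or about 1 to 6.5 subjects among 77 (the Cohort 1 minimum). With p = 44% the f = 1 range is 2.2-10.9 points; with p = 50% it is 2.4-12.0.

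**Simulation under the same null** (4,000 trials per setting; 24 months of follow-up; N = 77 or 134; 30% or 44% responders; assumed 12-month cystectomy-free rate 50-90%). Analysed from first dose, the median hazard ratio, responders to non-responders, was 0.70-0.79 at f = 1, 0.82-0.89 at f = 0.5 and 0.96-1.01 at f = 0. Restricted to subjects with the bladder intact at Day 91 and analysed from there, it was 0.96-1.02 throughout, so the landmark removes the distortion.

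**The case against.** **Early cystectomies may be rare.** No disease evaluation is scheduled between the start of dosing and Week 12-13, and the Protocol's introduction says "cystectomy is recommended for CIS and high-grade Ta and T1 patients who experience disease recurrence following intravesical therapy", so most surgery should follow an assessed failure. This stands. A reader might infer that the layout always produces a gap in favour of responders; it does so only to the extent that cystectomies precede the evaluation, and the documents do not say how many will.

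**Early deaths and losses.** It is tempting to count these as a further penalty on non-responders. The SAP censors both, so they reduce the number at risk but do not lower the curve, provided that such censoring is unrelated to cystectomy risk.

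**The responder curve is not strictly flat by construction.** The Protocol makes cystectomy a reason to stop study drug, which is not necessarily study discontinuation. A subject with an early cystectomy not recorded as study discontinuation, and without failing pathology or cytology, would default to complete responder under the last rule of SAP Section 5.2.1. This is correct, and another reason to define responder for these outputs.

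**The output is descriptive.** The tables are headed as proposed, the comparison is not a listed endpoint, and no test is named for it. A reader might infer an inflated false-positive rate. SAP Section 5 leaves room for testing unspecified further efficacy endpoints, but an error rate would apply only if a test were added here.

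**A landmark does not yield a drug effect.** Responders may have a better prognosis, and failure stops treatment and may itself lead to cystectomy. A landmark removes the guaranteed time, not that association.

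**Conclusion.** The point holds, with a size that cannot be fixed from the documents. As planned, the table and figure favour responders whenever cystectomies occur before the post-induction evaluation and are classed as non-response. With 40% complete response, no true link and 5-30% annual cystectomy, the artefact at 12 months is 2.0-10.3 points if the early hazard equals the later one, 1.0-5.4 points at half of it, and nil with no early cystectomy. The rates and hazard ratios are assumptions.

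The documents do not support extending the criticism to the main cystectomy-free-days analysis, which does not divide subjects by response. Nor do they support calling this a flaw in a confirmatory result. It concerns one supportive table and one figure; the priority is low to moderate.

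**What to change.** For Table 14.2.4.6 and Figure 14.2.4.2.2, state in the SAP:

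1. Responder means complete response at the post-induction (Month 3) evaluation.
2. The comparison includes only CIS subjects who are alive, in follow-up and with the bladder intact at that evaluation.
3. Time starts at the evaluation: Week 13 (about Day 91) or the subject's own evaluation date. Day 137, the end of the analysis window, serves at most as a sensitivity landmark. As the main origin it would drop cystectomies in the roughly 46 days (137 − 91) after a Week 13 failure, which may be genuine consequences of non-response.
4. Cystectomies, deaths and losses before the evaluation are listed separately.
5. A footnote says that the comparison is descriptive and carries no p-value, because failure stops treatment and may itself lead to cystectomy.

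The cost is a few lines of SAP text and no new data. Subjects with an event or loss before the evaluation leave this comparison but stay in the main cystectomy analysis.
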